2. OBJECTIVES

Primary Objectives:

To study the effect of deep neuromuscular block compared to standard neuromuscular block on intra-operative adverse events during laparoscopic surgery using the CLASSIC score system; see Table 2.

Secondary Objectives:

To study the effect of deep neuromuscular block as compared to standard neuromuscular block on:

- Surgical working conditions (using the validated Leiden surgical rating scale: L-SRS, Table 3)
- 30-day post-operative complications (using the Clavien-Dindo classification, Table 6)
- 30-day post-operative complications according to the Comprehensive Complication Index (<https://www.assesssurgery.com/>)
- 30-day unplanned readmission rates
- Quality of recovery at post-operative day 1, 2 and 30 after laparoscopic surgery.
 - Quality-of-recovery (QoR-40 questionnaire at postoperative day 1 and 2 (Appendix 1))
 - Quality-of-life at postoperative day 30 (SF36 questionnaire, Appendix 2)

Primary hypothesis:

Deep neuromuscular blockade reduces the incidence of intra-operative adverse events as measured by the CLASSIC score during laparoscopic surgery as compared to standard neuromuscular blockade.

Secondary hypotheses:

Deep neuromuscular blockade improves surgical working conditions and the early quality of recovery and reduces 30-day post-operative complications and unplanned readmissions after laparoscopic surgery, as compared to standard neuromuscular blockade.

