Grade II	Requiring pharmacological treatment with drugs other than such allowed for grade I complications. Blood transfusions and total parenteral nutrition are also included
Grade III	Requiring surgical, endoscopic or radiological intervention IIIa Intervention not under general anaesthesia IIIb Intervention under general anaesthesia
Grade IV	Life-threatening complication (including CNS complications)‡ requiring IC/ICU IVa Single organ dysfunction (incl. dialysis) IVb Multi organ dysfunction
Grade V	Death of a patient
Suffix 'd'	If the patient suffers from a complication at the time of discharge, the suffix 'd' (for 'disability') is added to the respective grade of complication.

‡ brain haemorrhage, ischaemic stroke, subarachnoidal bleeding, but excluding transient ischaemic attacks (TIA); IC: Intermediate care; ICU: Intensive care unit

Other postoperative measurements

Pain scores (NRS) at movement (and rest) three times daily at the ward until discharge or to a maximum of 72 hours, which will be extracted from the patient clinical charts.

Adverse events on the ward will be evaluated daily at hospitalization until discharge by a blinded researcher using the Clavien Dindo scale.

The quality of recovery score (QOR-40 questionnaire, appendix 1)[22] are filled in by the patient at day 1 and 2 after surgery.

30 days after surgery, a blinded researcher will evaluate any unplanned readmissions. In addition, patients will be contacted whether or not they have been readmitted in this period in any other hospital.

Also the SF36[23] questionnaire will be taken during this contact.

Additionally, the Comprehensive Complication Index (<https://www.assessurgery.com/>) will be used to grade postoperative complications [24]

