10.2 Secondary study parameters

Continuous normally distributed variables will be expressed by their mean and standard deviation or when not normally distributed as medians and their interquartile ranges. Categorical variables will be expressed as n (%). To test groups Student's t test will be used, if continuous data are not normally distributed the Mann-Whitney U test will be used. Categorical variables will be compared with the Chi-square test or Fisher's exact tests. P-values < 0.05 will be considered significant for the primary outcome. A cut off p-value of < 0.01 will be applied for secondary outcomes.

Data analysis will be performed using R Studio, Boston, MA, USA..

Longitudinal data (heart rate, blood pressure, L-SRS, BIS levels compared to the depth of NMB at the given moment) will be analyzed using linear mixed models. NONMEM (ICON Development Solutions, Ellicott, MD, USA), will be used for statistical analysis.

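### Section 10.2 leaves QoR-40 on days 1 and 2 to separate default tests, with no deciding comparison for the single early-recovery hypothesis and no use of the baseline score

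*Combined protocol and SAP*

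**What the plan says.** Section 2 states one secondary hypothesis on this matter: "Deep neuromuscular blockade improves surgical working conditions and the early quality of recovery". It singles out no day. The objectives fix the instrument and its timing: "Quality-of-recovery (QoR-40 questionnaire at postoperative day 1 and 2 (Appendix 1". Section 8.3 says that the forms "are filled in by the patient at day 1 and 2 after surgery", and that a baseline QoR-40 is taken before surgery and randomization. Section 8.1.1 also lists the Aldrete score at the PACU under quality of recovery.

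Three rules in section 10.2 apply:

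- Default test for continuous outcomes: "To test groups Student's t test will be used, if continuous data are not normally distributed the Mann-Whitney U test will be used".
- Level: "A cut off p-value of < 0.01 will be applied for secondary outcomes".
- Mixed models: "Longitudinal data (heart rate, blood pressure, L-SRS, BIS levels compared to the depth of NMB at the given moment". The bracketed list carries no wording that marks it as examples, and QoR-40 is absent.

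Section 10 does not say which QoR-40 day decides, whether the days are combined, whether baseline enters the analysis, or how missing forms are handled.

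**The concern.** QoR-40 is measured three times in the same patient: at baseline, day 1 and day 2. A statistician who follows section 10.2 as written would nevertheless run two unadjusted two-sample comparisons. The test, and with it the summary measure, could differ between the days if the distributions differ. One hypothesis would then face two p-values and no decision rule.

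What is at stake depends on the rule adopted later. If a result on either day is taken as support, the 0.01 level no longer holds for the claim. If one day is chosen, the information in the other day is lost. Under both rules the baseline score is collected and then not used.

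There is also a gap in collection. The plan foresees that some patients leave hospital within 72 hours, since ward pain scores run "three times daily at the ward until discharge or to a maximum of 72 hours". The only contact after discharge described in section 8.3 is at day 30, and no route is given for returning a day-2 form from home.

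**Working it through.** **Inputs from the documents.** 439 per arm (section 4.4); 0.01 level for secondary outcomes (section 10.2); QoR-40 at baseline and on days 1 and 2 (sections 2 and 8.3).

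**Assumptions, because the documents give no figure.** Two-sided testing; effect d = 0.2 SD, equal on both days; correlation between days ρ = 0.5 to 0.8; correlation of each day with baseline r = 0.5 where baseline is used. Normal approximation throughout.

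**1. The plan's own figure.** For 20% against 12% (a 40% relative reduction), 5% two-sided and 90% power:
n = [1.960·√(2·0.16·0.84) + 1.282·√(0.20·0.80 + 0.12·0.88)]² / 0.08² = (1.016 + 0.660)² / 0.0064 ≈ 439 per arm (440 if rounded up). Then 878 × 1.05 ≈ 922. The stated size is reproduced. It concerns the primary endpoint only; no power is stated for QoR-40.

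**2. One day decides.** Expected z = d·√(n/2) = 0.2·√219.5 = 2.963. The critical value is 2.576. Power = Φ(2.963 − 2.576) = Φ(0.387) = 65%, with error 1%.

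**3. Either day may decide.** The two z-values are bivariate normal with correlation ρ. False-positive chance = 1 − P(both |z| < 2.576 under no effect). Power = 1 − P(both z < 2.576 with mean 2.963).

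**4. Two-day average, one test at 1%.** The SD shrinks by √((1+ρ)/2). Power = Φ(2.963/√((1+ρ)/2) − 2.576).

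| ρ | Either day: error | Either day: power | Average: error | Average: power |
|---|---|---|---|---|
| 0.5 | 1.90% | 80% | 1% | 80% |
| 0.6 | 1.85% | 79% | 1% | 77% |
| 0.7 | 1.77% | 77% | 1% | 74% |
| 0.8 | 1.66% | 75% | 1% | 71% |

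**5. Like for like at 1%.** If the either-day rule is held to 1% in total by testing each day at 0.005 (critical value 2.807), the formula of step 3 gives power of 73% (ρ = 0.5) to 66% (ρ = 0.8), below the average in each case.

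**6. Adding baseline.** The variance of the adjusted two-day mean is (1+ρ)/2 − r². With r = 0.5:

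- ρ = 0.5: SD = √0.50 = 0.707; Φ(4.190 − 2.576) = 95%.
- ρ = 0.7: SD = √0.60 = 0.775; Φ(3.825 − 2.576) = 89%.
- One day alone with baseline: SD = √0.75 = 0.866; Φ(3.422 − 2.576) = 80%.

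**7. Missing day-2 forms.** No rate is given. With a fraction m missing, n becomes 439(1 − m). Day-2 power is 59%, 53% and 46% for m = 10%, 20% and 30%. A likelihood model that also uses day 1 has day-2 variance proportional to ρ² + (1 − ρ²)/(1 − m). Power becomes 56-59% at m = 20% and 50-54% at m = 30% (ρ = 0.5 to 0.7), so only part of the loss is recovered.

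**The case against.** **The list may be illustrative, and the sentence concerns other data.** The mixed-model sentence covers series set against depth of block at the same moment, which reads naturally as intraoperative. That supports giving QoR-40 its own sentence. It does not supply a deciding comparison.

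**Day-specific comparisons are legitimate.** Days 1 and 2 are named time points, and an average is less sensitive to a benefit on one day only. This stands as a reason to report both days. It does not remove the need to say in advance which result settles the hypothesis.

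**The error is small, and the either-day rule is not weak.** This stands in part. Two tests at 0.01 cannot exceed 2%, and either-day power equals or slightly exceeds that of the average. It does so only by spending the extra error (step 5). A reader might add the raised error to the 65% power; they belong to opposite decision rules and cannot both apply.

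**Baseline adjustment does as much as averaging.** True at r = 0.5: each alone lifts 65% to 80% (for averaging, at ρ = 0.5). The fix should therefore include baseline.

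**Loss of patients who have gone home.** A reader might infer that the day-2 comparison excludes discharged patients. The documents do not support this. The limit at discharge governs ward pain scores, medication use and daily ward review; QoR-40 is completed by the patient with no restriction to inpatients. What remains is a risk, because no route for returning forms is described. An illustrative simulation shows the direction only. It assumed a true effect of 0.25 SD, 20% of controls discharged before day 2, day-to-day correlation 0.6, and discharge driven by a latent recovery correlated 0.8 with the day-2 score. The completed-form difference was 0.16 SD if no discharged patient returned a form and 0.22 SD if half did. Using day 1 gave 0.18 and 0.23 SD, so the model alone does not repair such a loss. These inputs are chosen, and none comes from the documents.

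**Conclusion.** The point holds in a limited form. Section 10.2 gives the early-recovery hypothesis two default QoR-40 tests, no deciding comparison and no use of the baseline score. The main defect is the undefined decision rule; lost precision comes second, and inflation of error is modest.

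The cost is either a false-positive chance 0.7 to 0.9 percentage points above the intended 1%, or about 6 to 15 points of power against the two-day average (65% against 71-80%), but not both. Baseline adjustment would bring the average to about 89-95% power at an assumed baseline correlation of 0.5 and ρ from 0.7 down to 0.5. All these figures rest on an assumed 0.2 SD effect and assumed correlations.

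That tests will be confined to completed forms is itself an inference from silence on missing data, and discharge-related loss is a risk of unknown size. The primary endpoint and the sample size are untouched. This is a minor-to-moderate improvement to one secondary outcome.

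**What to change.** **Section 10.2, as a separate sentence or two:** analyze QoR-40 on days 1 and 2 in one linear mixed model with arm, day, arm-by-day and baseline QoR-40, adjusted for the stratification factors (center and BUPA category) and including every patient with at least one postoperative form. Make the arm effect averaged over both days, with its confidence interval, the one QoR-40 test at 0.01. Report the day-specific differences as description. Keep the PACU Aldrete score as a separate measure. State the assumption made about missing forms.

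**Section 8.3, one sentence:** give patients discharged before day 2 the form to take home, or send it electronically.

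**Cost:** a few sentences, with no new instrument and no additional patients; the plan already uses linear mixed models. The downsides are less sensitivity to a benefit confined to one day, reliance on missing forms being explained by the observed data (missing at random), and only partial recovery of information when day-2 forms are missing. The last is why the collection route matters as well as the model.

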5. TREATMENT OF SUBJECTS

There are no specific study-related pre-study requirements. On the day of surgery, patients will be randomized between the two treatment groups. Anesthesia and postoperative care follow routine local protocol, apart from neuromuscular management. Neuromuscular management during surgery depends on the treatment allocation; patients will be randomized between one of the following groups:

Group 1 (experimental): Deep neuromuscular block.

- Muscle relaxation with rocuronium (Esmeron, MSD BV), target depth: post-tetanic-count of 1-2 twitches from start of surgery until the end
- Induction dose rocuronium: 0.6 – 1.0 mg/kg, aimed at PTC 1-2 at surgery start
- Maintenance: continuous infusion of rocuronium at 0.2-0.6 mg/kg/hr, titrated to maintain PTC 1-2
- Reversal of NMB with sugammadex 4 mg/kg at the end of surgery

Group 2 (comparator): standard care

- Muscle relaxation with rocuronium (Esmeron, MSD BV), target depth: train-of-four count of > 0 twitches from start of surgery until the end.
- Induction dose rocuronium: 0.3-0.6 mg/kg, aimed at a TOF count of > 0 twitches at surgery start
- Repeated doses of rocuronium 10 mg on request by the surgeon only
- Reversal of NMB with sugammadex 2 mg/kg at the end of surgery, when TOF ratio < 0.9 at surgery end.

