8.1.1 Secondary study parameters/endpoints

To study the effect of deep neuromuscular block as compared to standard neuromuscular block on:

- Surgical working conditions (L-SRS, Table 3)
- 30-day post-operative complications (Clavien-Dindo, Table 6)
- 30-day post-operative complications according to the Comprehensive Complication Index
- 30-day unplanned readmission rates
- Quality of recovery at post-operative day 1, 2 and 30 after laparoscopic surgery.
 - Quality-of-recovery (QoR-40 at postoperative day 1 and 2; Aldrete score (Table 5) at the PACU)
 - Quality-of-life at postoperative day 30 (SF36, Appendix 2)

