8.1.2 Other study parameters

- Patient age, gender, length and weight, ASA class, underlying disease(s), planned procedure, blood pressure and heart rate, center of admission
- Pre-operative NRS, QoR-40 and SF 36
- Per operative the following variables will be noted, after installation of the pneumoperitoneum at 15 minute intervals until the end of the surgery. At these moments the L-SRS is also scored:
 - Heart rate (/min), blood pressure in mmHg
 - Intra-abdominal pressure in mmHg and total insufflations volume (in Liters)
 - Depth of anesthesia: Bispectral Index and end-tidal sevoflurane
 - Depth of NMB (TOF count and/or PTC)
 - Duration of surgery and anesthesia
 - Time of extubation
 - Cumulative drug dosages (propofol, opioids, muscle relaxant, reversal agent, inotropics, NSAIDS's or metamizol)
 - Core temperature in degrees Celsius
 - Surgical satisfaction with the anesthesia: 'very dissatisfied', 'dissatisfied', 'satisfied' tot 'very satisfied'.
- Postoperative recovery scores:
 - Time to discharge readiness (Aldrete score ≥ 9 and NRS < 5)
 - Heart rate (/min), blood pressure in mmHg
 - peripheral oxygen saturation, respiratory rate (/min), use of supplemental O₂ (in liters/minute)
 - NRS and administration of analgesic medication
 - Ramsay sedation scale and Aldrete score
 - Nausea or vomiting

- Length of admission at the PACU and/or ICU (if applicable) and duration of hospital admission
 - Pain scores (numeric rating scale; NRS 0 no pain – 10 worst pain imaginable) at movement (and rest) three times daily until discharge or to a maximum of 72 hours will be extracted from the patient clinical charts.
 - Medication use (three times daily until discharge or to a maximum of 72 hours) will be extracted from the patient clinical charts.
 - Cumulative opiate use
 - Cumulative use of other analgesics and anti-emetics

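### Section 10.2 states no randomised-arm term for the repeated L-SRS scores and, on its more natural reading, models them against momentary depth of block

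*Combined protocol and SAP*

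**What the plan says.** Section 2 introduces the secondary objectives with "To study the effect of deep neuromuscular block as compared to standard neuromuscular block on" and lists surgical working conditions first. Section 8.1.1 repeats this as "Surgical working conditions (L-SRS, Table 3". The question is therefore a comparison of the randomised arms.

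L-SRS is a 1-5 score given by the blinded surgeon every 15 minutes (section 8.3). Section 8.1.2 lists the variables noted at those intervals, says "At these moments the L-SRS is also scored", and includes "Depth of NMB (TOF count and/or PTC" among them.

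Section 10.2 contains two rules that could apply:

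- A generic rule for secondary variables: "To test groups Student's t test will be used, if continuous data are not normally distributed the Mann-Whitney U test will be used". Secondary outcomes are judged at p < 0.01.
- A separate paragraph on longitudinal data, which names L-SRS: "L-SRS, BIS levels compared to the depth of NMB at the given moment) will be analyzed using linear mixed models". NONMEM is named as the software.

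Section 5 sets the depth targets on different scales. Group 1 has "target depth: post-tetanic-count of 1-2 twitches from start of surgery until the end" and Group 2 has "target depth: train-of-four count of > 0 twitches from start of surgery until the end". In Group 2, further rocuronium is given at the surgeon's request. Section 8.3 lists extra rocuronium among the measures that may be taken when L-SRS deteriorates.

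**The concern.** The objective asks what assignment to deep block does to L-SRS. The one analysis sentence that names L-SRS mentions momentary depth of block and not arm. Depth is not a stand-in for arm, for three reasons:

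- It is observed after randomisation, so a regression on it is not protected by randomisation.
- It can respond to the outcome. A poor score may prompt rocuronium, which deepens the block at the next reading.
- It has no stated unit. TOF count and PTC are different scales, and the plan gives no rule for combining them.

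As written, the plan does not settle which L-SRS result is the randomised comparison. The analyst could report a depth coefficient, or one of several per-patient summaries, chosen after seeing the data. A depth coefficient reported for the first secondary objective would answer a different question. It could also be biased if serial correlation within a patient is left out, and 10.2 names no covariance structure.

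**Working it through.** **The plan's own figure.** The documents give no sample size, variance or target difference for L-SRS. The only design figure is for the primary endpoint (section 4.4): 20% versus 12%, alpha 5%, 90% power, 439 per arm. With pooled variance and a two-sided test:

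n = [1.960 × √(2 × 0.16 × 0.84) + 1.282 × √(0.20 × 0.80 + 0.12 × 0.88)]² / 0.08² = (1.016 + 0.660)² / 0.0064 ≈ 439

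This reproduces the plan's number and does not depend on the L-SRS analysis. It is used below only to set 439 patients per arm.

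**Reading the sentence.** There are two ways to attach the words about depth.

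| Reading | L-SRS model | Arm term stated? |
|---|---|---|
| Depth applies to the whole list | L-SRS on depth at the same moment | No |
| Depth applies to BIS only | Mixed model with no stated terms | No |

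The first is more natural: nothing separates BIS from the rest of the list, and L-SRS is scored at the same moments as depth. The arm term is absent on both.

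**Is depth post-randomisation and responsive to L-SRS?** Randomisation is just before surgery (section 8.2) and depth is recorded during surgery (8.1.2). Rocuronium may follow a fall in L-SRS (8.3) or a surgeon's request in Group 2 (5). Both answers are yes.

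**Illustrative simulation.** Except for the 439 per arm, all inputs are assumptions:

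- 878 patients, 8 readings each. Latent score 4.0 + b × (depth − 0.2), patient SD 0.6, AR(1) residual SD 0.5 with correlation 0, 0.3 or 0.7, rounded to 1-5. About 20-26% of standard-arm scores were 3 or lower.
- Depth on a 0-1 scale. Deep arm at 1. Standard arm flat at 0.2, or recovering from 0.5 by 0.1 per interval to 0.
- After a standard-arm score of 3 or lower, depth rises to 0.9 with probability 1, 0.5 or 0.25 (recovering case: 1 or 0.25), then falls 0.35 per interval to its base.
- b = 0, 0.25 or 0.5, giving 45 scenarios of 100 runs each. Monte Carlo SE of mean coefficients at most 0.004.
- REML fits: depth with a random intercept only; depth + time with random intercept, AR(1) and measurement error; arm + time with the same covariance as the second.

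*Different quantity.* With serial correlation modelled, flat standard-arm depth and b = 0.5, at correlation 0 / 0.3 / 0.7:

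| Low scores followed by rocuronium | Depth coefficient | Arm difference |
|---|---|---|
| Every | 0.467 / 0.455 / 0.475 | 0.266 / 0.269 / 0.277 |
| A quarter | 0.455 / 0.455 / 0.472 | 0.323 / 0.324 / 0.325 |

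For example, 0.467 / 0.266 = 1.76 and 0.455 / 0.324 = 1.40. Over all scenarios with b = 0.5, depth coefficients were 0.44 to 0.48 and arm differences 0.26 to 0.33. With b = 0.25 they were 0.23 to 0.24 and 0.14 to 0.17. The ratio was 1.4 to 1.8.

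Hand check: the arm difference is about b × (1 − m), where m is mean standard-arm depth, so the ratio is about 1 / (1 − m). Here m was 0.25 to 0.41, giving 1 / 0.75 = 1.33 to 1 / 0.59 = 1.69, before rounding and the ceiling at 5.

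*Bias with no true effect (b = 0), random intercept only.* Depth coefficient at correlation 0 / 0.3 / 0.7:

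| Standard-arm depth | Low scores followed by rocuronium | Depth coefficient |
|---|---|---|
| Flat | Every | 0.01 / -0.15 / -0.31 |
| Flat | Half | 0.00 / -0.09 / -0.19 |
| Flat | A quarter | 0.00 / -0.06 / -0.12 |
| Recovering | Every | 0.00 / -0.13 / -0.25 |
| Recovering | A quarter | 0.00 / -0.04 / -0.08 |

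The sign follows from the feedback: a low score prompts rocuronium, and the next score, still low through serial correlation, is paired with a deeper block. With serial correlation modelled, the depth coefficient lay between -0.012 and 0.010 in all 15 null scenarios. That fit also adds time, but the simulated score has no time trend when b = 0, so the time term does not explain the change. The arm model averaged 0.003 or less in every null scenario.

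**The case against.** The strongest reply is that an arm comparison is already planned. L-SRS is a secondary parameter, section 10.2 covers secondary parameters, and its generic t test or Mann-Whitney rule at p < 0.01 therefore applies. The longitudinal paragraph, with different software, can then be read as a supplementary exposure-response analysis. Nothing in the plan says that the depth coefficient will be reported for the objective. This stands in part: an arm comparison is not excluded. But the generic rule does not say how 15-minute scores become one value per patient, and the sentence that names L-SRS sends it to another method.

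Second, the words about depth may belong to BIS only. If so, the feedback, scale and bias arguments fall away for L-SRS, and what remains is a mixed model with no stated contrast. The gap is still there.

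Third, the simulation is not evidence about this trial. The ratio compares coefficients in different units and changes with the depth scale, and depth could instead enter as categories. The null bias needs a random-intercept-only model, which the plan does not specify. The largest value needs rocuronium after every low score, although section 8.3 makes it one of four optional measures. All of this is right, so the figures show only that the two quantities differ and which way bias would run.

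Fourth, a mixed model is not the only remedy. A defined per-patient summary for the tests already named, or an ordinal model for a 1-5 score, would also serve. That is accepted.

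**Conclusion.** The concern holds. For the first secondary endpoint, section 10.2 states no randomised-arm term for the repeated scores. The only comparator it names, on the more natural reading, is a post-randomisation variable that can respond to the outcome and has no common scale. This rests on the text and on neither the simulation nor the choice of reading, because the arm term is missing on both.

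The size cannot be estimated from the documents. Under the stated assumptions the depth coefficient was 1.4 to 1.8 times the arm difference, and spurious effects reached -0.31 points per unit of assumed depth if serial correlation was ignored. That bias is conditional on the omission; the difference in meaning is not. The point should be corrected, but it concerns a secondary endpoint only and leaves the primary analysis and sample size untouched.

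**What to change.** In section 10.2, state that L-SRS is compared as randomised by a linear mixed model with:

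- randomised arm as the effect of interest;
- time as a fixed effect;
- a patient random effect, with a residual structure that allows for serial correlation;
- a test at the 0.01 level already set for secondary outcomes.

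Adjustment for the stratification factors (centre and BUPA category) is optional. If the sponsor prefers the group tests already named, 10.2 should define in advance the single per-patient L-SRS value to which they apply.

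Label the model against momentary depth of block as an exploratory exposure-response analysis, and say whether depth enters as TOF count, PTC or a defined combined scale.

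The cost is analysis wording only, with the same data and software and no added patients or visits.
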